4.1 Inclusion Criteria

- 4.1.1** Patients \geq 18 years old.
- 4.1.2** Histologically confirmed diagnosis of squamous cell carcinoma of the oral cavity, oropharynx, larynx, or hypopharynx AJCC 7th edition stages III, IVa, or IVb, p16-negative on immunohistochemistry (p16 testing to be performed only on oropharynx cancers, as it has not been found to be prognostic or standard of care outside of cancers of the oropharynx).
- 4.1.3** Determined by the treating physician to be a candidate for organ preserving, concurrent standard chemotherapy and radiation therapy to the head and neck with definitive intent.
- 4.1.4** ECOG Performance Status 0-2
- 4.1.5** Patients must sign an informed consent document that indicates they are aware of the investigational nature of the treatment in this protocol as well as the potential risks and benefits.
- 4.1.6** Ability to understand and the willingness to sign a written informed consent.

4.2 Exclusion Criteria (All laboratory studies must be completed 1 month prior to signing consent)

- 4.2.1** Prior radiation therapy (defined as more than 5 fractions of head and neck radiotherapy, less than 10 Gy total prior radiation) to the head and neck
- 4.2.2** Prior chemotherapy within the past 5 years
- 4.2.3** Previous therapy with a human immunodeficiency virus (HIV) protease inhibitor
- 4.2.4** Females who are pregnant at the time of screening will not be eligible for this study, urine pregnancy test will be performed at screening and prior to injection of FMISO in women of child-bearing potential.
- 4.2.5** Patients with known HIV disease. These patients have a high probability of treatment with anti-retroviral therapy which may interact with the nelfinavir.
- 4.2.6** Absolute Neutrophil Count \leq 1500 per mm³
- 4.2.7** Platelet count \leq 100,000 per mm³
- 4.2.8** Serum creatinine $>$ 1.5 times the upper limit of normal
- 4.2.9** Serum AST or ALT $>$ 2 times the upper limit of normal
- 4.2.10** Serum bilirubin $>$ 1.2 mg/dl
- 4.2.11** Weight loss of $>$ 10% over the past 6 months which is due to tumor wasting syndrome
- 4.2.12** Distant metastases
- 4.2.13** Patients receiving the following drugs that are contraindicated with NFV will be excluded.

Antiarrhythmics: amiodarone, quinidine	CONTRAINDICATED due to potential for serious and/or life threatening reactions such as cardiac arrhythmias

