PDE5 Inhibitors: sildenafil, vardenafil, tadalafil	↑ PDE5 inhibitors	Concomitant use of PDE5 inhibitors and VIRACEPT should be undertaken with caution. If concomitant use of PDE5 inhibitors and VIRACEPT is required, sildenafil at a single dose not exceeding 25 mg in 48 hours, vardenafil at a single dose not exceeding 2.5 mg in 72 hours, or tadalafil at a single dose not exceeding 10 mg dose in 72 hours, is recommended.

HMG-CoA Reductase Inhibitors: atorvastatin, rosuvastatin	↑ atorvastatin ↑ rosuvastatin	Use lowest possible dose of atorvastatin or rosuvastatin with careful monitoring, or consider other HMG-CoA reductase inhibitors such as pravastatin or fluvastatin in combination with VIRACEPT.
Immuno- suppressants: cyclosporine, tacrolimus, sirolimus	↑ immuno- suppressants	Plasma concentrations may be increased by VIRACEPT.
Narcotic Analgesic: methadone	↓ methadone	Dosage of methadone may need to be increased when coadministered with VIRACEPT.
Oral Contraceptive: ethinyl estradiol	↓ ethinyl estradiol	Alternative or additional contraceptive measures should be used when oral contraceptives and VIRACEPT are coadministered.
Macrolide Antibiotic: azithromycin	↑ azithromycin	Dose adjustment of azithromycin is not recommended, but close monitoring for known side effects such as liver enzyme abnormalities and hearing impairment is warranted.
Inhaled/nasal steroid: fluticasone	↑ fluticasone	Concomitant use of fluticasone propionate and VIRACEPT may increase plasma concentrations of fluticasone propionate. Use with caution. Consider alternatives to fluticasone propionate, particularly for long-term use.
Antidepressant: trazodone	↑ trazodone	Concomitant use of trazodone and VIRACEPT may increase plasma concentrations of trazodone. Adverse events of nausea, dizziness, hypotension and syncope have been observed following coadministration of trazodone and nelfinavir. If trazodone is used with a CYP3A4 inhibitor such as VIRACEPT, the combination should be used with caution and a lower dose of trazodone should be considered.

4.2.16 Women of childbearing potential who have a positive result on screening urine pregnancy test.

4.2.17 Subjects with moderate-severe renal disease.

4.2.18 History of allergic reactions attributed to Flagyl (metronidazole), which has a chemical structure similar to FMISO.

4.2.19 Uncontrolled intercurrent illness including, but not limited to symptomatic congestive heart failure, unstable angina pectoris, or psychiatric

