4.5 Clinical Evaluation and Staging Criteria

- History and Physical Examination
- Laboratory studies: CBC with differential, Comprehensive metabolic panel, pregnancy tests for women of child bearing age or potential.
- Staging studies are to include a chest x-ray, chest CT, or FDG PET scan to evaluate for systemic metastases, performed within 12 weeks prior to study entry.

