- Change to the protocol taken without prior IRB review to eliminate apparent immediate hazard to a research participant.
- Incarceration of a participant when the research was not previously approved under Subpart C and the investigator believes it is in the best interest of the subject to remain on the study.
- Complaint of a participant when the complaint indicates unexpected risks or the complaint cannot be resolved by the research team.
- Protocol violation (meaning an accidental or unintentional deviation from the IRB approved protocol) that in the opinion of the investigator placed one or more participants at increased risk, or affects the rights or welfare of subjects.
- **Exceptions:** A study exception is a one time, intentional action or process that departs from the IRB and CTSRMC approved study protocol, intended for one occurrence. If the action disrupts the study progress, such that the study design or outcome (endpoints) may be compromised, or the action compromises the safety and welfare of study subjects, advance documented IRB and DSMC approval is required. For this in-house study with a sponsor monitor, approval will be obtained from the study sponsor (IND Support Office) prior to submitting the exception request to the IRB and DSMC.
- **Deviations:** A study design deviation is a one time, unintentional action or process that departs from the IRB and CTSRMC approved study protocol,

involving one incident and identified retrospectively, after the event occurred. If the impact on the protocol disrupts the study design, may affect the outcome (endpoints) or compromises the safety and welfare of the subjects, the deviation will be reported to the DSMC and IND Support Office within 5 business days and the IRB within 10 business days.

8.2 $^{18}\text{F-FMISO}$ and FDG PET/CT

Pregnancy Clause

The effects of $^{18}\text{F-FMISO}$ on unborn children, children who are breast-feeding and the health of the mother are unknown. For this reason, subjects who are pregnant must inform the investigator(s) and understand that she will not be included in the study. Women of childbearing age will have a pregnancy test before making a decision about participating in the study. The cost of the exam is part of regular cancer care and may be done even they do not join the study.

IV Contrast Risks & Procedures Clause

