8.3.1 Pregnancy Clause

Because of the effects of Nelfinavir, there could be serious harm to unborn children or children who are breast-feeding. These effects could also harm the mother. It is also possible that harmful side effects that are not yet known could happen to both the mother and unborn or breast-feeding child. If you are currently pregnant, it is important that you inform the investigator(s) because you will not be able participate in the study. If you are able to become pregnant, you will be given a urine pregnancy test before entry into the study. You are asked to use a medically accepted method of birth control (such as condoms, vasectomy, abstinence) while you participate in the study. You should not become pregnant while you are taking this drug. If you do become pregnant, you must discontinue the drug, tell the investigator and consult an obstetrician or maternal-fetal specialist.

If you are a man, you are advised to use a means of birth control (such as condoms, abstinence, vasectomy) while you are taking part in this study because the effect of treatment on your sperm or upon the development of an unborn child is not known. You should not father any children while on this study.

9 Data Handling and Record Keeping

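### Sections 8.2 and 8.3.1 name a risk to breast-fed children, but the visible entry criteria in 4.2 bar only pregnancy

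*Combined protocol and SAP*

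**What the plan says.** Two exclusions in section 4.2 deal with reproductive status. Exclusion 4.2.4 states "Females who are pregnant at the time of screening will not be eligible for this study" and schedules a urine test at screening and before FMISO injection. Exclusion 4.2.16 lists "Women of childbearing potential who have a positive result on screening urine pregnancy test". In section 4.5 the only related screening item is "pregnancy tests for women of child bearing age or potential", and section 6.5 repeats the pregnancy test before each FMISO scan.

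The risk statements are in section 8. The pregnancy clause of 8.2 says that the effects of FMISO "on unborn children, children who are breast-feeding and the health of the mother are unknown". It gives that uncertainty as its ground and goes on: "subjects who are pregnant must inform the investigator(s) and understand that she will not be included in the study". Section 8.3.1 says that, because of nelfinavir's effects, "there could be serious harm to unborn children or children who are breast-feeding". It follows with "If you are currently pregnant, it is important that you inform the investigator(s) because you will not be able participate in the study", asks for contraception, and sets out what a woman should do if she becomes pregnant.

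**The concern.** Each clause in section 8 names two kinds of children at risk, the unborn and the breast-fed. Each then draws a consequence for entry that covers only the first. Section 4.2 follows the same pattern: pregnancy is addressed twice and breast-feeding not at all. The conclusion is narrower than the reason given for it.

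What is at stake is the safety of a third party. A nursed infant could be exposed to a harm that the protocol itself describes as possibly serious (nelfinavir) or of unknown extent (FMISO), with no eligibility rule prompting anyone to ask. Nothing in the primary endpoint, the power statement or the imaging analyses depends on this.

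**Working it through.** The point concerns text, so the check is to set the passages side by side.

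| Place | Names a risk to breast-fed children? | Who is barred or tested |
|---|---|---|
| 8.2, pregnancy clause (FMISO) | Yes, unknown | Pregnant women barred |
| 8.3.1 (nelfinavir) | Yes, possibly serious | Pregnant women barred |
| 4.2.4 | No | Pregnant women barred; test at screening and before FMISO |
| 4.2.16 | No | Women with a positive screening test barred |
| 4.5 | No | Pregnancy test only |
| 6.5 | No | Pregnancy test before each scan |
| 4.6 (off-study) | No | No reproductive criterion; investigator discretion |

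The count is 2 statements of risk to breast-fed children, 2 exclusions on pregnancy, and 0 listed criteria on breast-feeding. A negative pregnancy test says nothing about nursing, so the tests in 4.5 and 6.5 do not close the gap.

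**Does standard treatment make the point moot?** Not on the protocol's own sequence. Section 6.5 puts the first FMISO scan shortly after enrolment, before any therapy. Sections 5.2 and 6.2 start nelfinavir 7 to 14 days before chemoradiotherapy. Exposure to both study agents therefore begins before the standard treatment does. With 7 weeks of radiation (section 6.4), planned nelfinavir exposure is 1 + 7 = 8 to 2 + 7 = 9 weeks. Two FMISO scans are planned for most FMISO-imaged subjects and three for the six test-retest patients (section 1).

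**How many women could be concerned?** The accrual table in section 4.3 expects 6 women among 28 subjects. Sections 3.2 and 3.3 say the initial 15 subjects were imaged with EF5. Section 7 speaks of 28 patients starting with the amendment, which leaves open whether those 15 are inside the 28.

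- If they are outside: 6 women.
- If they are inside: 28 − 15 = 13 subjects remain, and 13 × 6/28 = 2.8, about 3 women.

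The documents give no figure for how many would be breast-feeding. My assumption is few or none.

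**The case against.** The strongest reply is that the copy reviewed is incomplete. Section 8.3.1 addresses the subject directly and reads like consent language. Section 4.1.5 requires a signed consent showing awareness of the risks, and section 11 says every subject receives a consent form. Those pages were removed, so an instruction about nursing may exist there. In addition, the numbering runs from 4.2.13 to 4.2.15. This may be a slip or lost text. Both limits stand, and the finding applies only to the criteria as shown. They do not remove it: a warning in a consent form is not an entry criterion, and the mismatch between 4.2 and section 8 is visible without it.

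A second reply is that clinical judgement already protects such a patient. Section 4.1.3 requires the treating physician to find her a candidate for concurrent chemotherapy and radiation, and section 4.6 lets the investigator take a patient off study at any time. A reader might infer that a breast-feeding woman meets every entry criterion. The documents do not support that, because she must still satisfy all the others, including 4.1.3. What remains is that these safeguards are discretionary, that 4.1.3 concerns standard treatment, and that neither names breast-feeding.

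Third, exposure is not certain even for an enrolled woman: section 3.1 allows a patient to be excused from the PET/CT requirement. That is correct, but it does not affect nelfinavir.

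Finally, a reader might infer that exclusion is the only possible answer, or that 4.2.16 merely repeats 4.2.4 and can go. Neither follows. The passages show that the texts must be reconciled, not which rule must result. And 4.2.4 turns on being pregnant, whereas 4.2.16 is the only criterion that explicitly makes a positive test exclusionary.

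**Conclusion.** The point holds in a limited form. Sections 8.2 and 8.3.1 identify breast-fed children as possibly at risk, while both clauses and the visible exclusions 4.2.4 and 4.2.16 act on pregnancy alone. Breast-feeding therefore does not by itself fail any listed entry criterion. This is an inconsistency between the protocol's stated reason and its rule, and it needs no outside source to establish.

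It is minor in likelihood, with about 3 to 6 women expected and few or none of them nursing, and it has no bearing on the sample size or analysis. It deserves correction because the possible harm falls on an infant. The conclusion rests on the criteria as visible, with no 4.2.14 and no consent pages. It does not establish that the trial as a whole leaves nursing mothers without any warning.

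**What to change.** Reconcile 4.2.4 with 8.2 and 8.3.1 so that the eligibility text explicitly addresses breast-feeding women as well as pregnant women. One way is to extend the existing pregnancy exclusion to breast-feeding and align the participation sentences in the two section 8 clauses. The final rule is for the sponsor to decide. Keep 4.2.16. While editing, the sponsor should confirm whether a 4.2.14 exists and check that the consent form agrees with the revised text.

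The cost is a few words in three places, with no new test or visit and a near-nil effect on accrual.

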4.3 Inclusion of Women and Minorities

The University of Pennsylvania Medical Center serves the metropolitan Philadelphia area, the surrounding suburban counties, southern New Jersey, and northern Delaware.

Inclusion of minorities: The University of Pennsylvania Cancer Center reports that minorities accounted for 14% of all patients (adult and pediatric) enrolled on therapeutic clinical trials. Furthermore, it is estimated that approximately 30% of cancer patients admitted to the Hospital of the University of Pennsylvania are minorities (source: University of Pennsylvania Cancer Center Grant). Female and male patients of all ethnic groups will be eligible for treatment in these protocols. Protocol accrual will be reviewed annually to include a determination of minority representation. An attempt will be made to enroll patients with larynx cancer in a distribution that matches the frequency of incident larynx cancer in the general population. The minority accrual estimates for our trial are based upon the total number of patients, the incidence rates of head and neck larynx cancer, and estimates in the literature regarding minority accrual in clinical trials. A study by Tejeda and Brawley (31) found that the accrual of American cancer patients to NCI-sponsored treatment trials paralleled the incident disease burden among minorities. A report by Sikora et al. (32) indicates the distribution of incident head and neck squamous cell carcinoma to be 81.8%, 21.1%, 11.9%, 5.2%, 3.7%, 0.3%, and 0.8% among whites, all minorities, blacks, Asians, Hispanics, others and unknowns, respectively. The Philadelphia metropolitan area does not have a large American Indian or Alaskan population; therefore, no patients are estimated for this group.

Inclusion of women: Recruitment of patients will be through the University of Pennsylvania Cancer Center, Department of Radiation Oncology. All patients meeting study requirements will be approached for participation without discrimination. According to Cancer Facts and Figures (2011) from the American Cancer Society (33), new cases of larynx cancer were divided approximately 4:1 among male and female patients. Based on these and the above minority data, we estimate the accrual distributions for this trial shown below:

Ethnic Category	Males	Females	Total
Hispanic or Latino	1	0	1
Not Hispanic or Latino	21	6	27
Ethnic Category Total of All Subjects	22	6	28
Racial Categories			
American Indian/Alaska Native	0	0	0
Asian	1	0	1
Native Hawaiian or other Pacific Islander	0	0	0
Black or African American	3	1	4
White	18	5	24
Racial Categories: Total of All Subjects	22	6	28

Proposed Outreach Programs

The University of Pennsylvania Cancer Center has developed a number of minority outreach strategies. These include development of relationships with local community organizations, presentations or distribution of materials to local groups regarding trials, advertisements in minority newspapers and magazines, and presentations to professional organizations. If under-accrual of minority subjects is determined to be a problem, we will employ these methods to improve accrual. We will also make an effort to educate radiotherapists, surgeons, and medical oncologists who are working within our network and who serve minority populations about this trial.

4.4 Subject Recruitment and Screening

Subjects will be recruited from the departments of Medical Oncology and Radiation Oncology. The consent process can be completed in person or via Telemedicine per University of Pennsylvania Health Systems telemedicine policy and procedures.

4.5 Clinical Evaluation and Staging Criteria

- History and Physical Examination
- Laboratory studies: CBC with differential, Comprehensive metabolic panel, pregnancy tests for women of child bearing age or potential.
- Staging studies are to include a chest x-ray, chest CT, or FDG PET scan to evaluate for systemic metastases, performed within 12 weeks prior to study entry.

4.6 Off-Study Criteria

- Extraordinary Medical Circumstances. If at any time the constraints of this protocol are detrimental to the subject's health, the subject will be removed from protocol therapy. In this event, the reasons for withdrawal will be documented.
- Subject's refusal to continue treatment. In this event, the reasons for withdrawal will be documented.
- Any patient who experiences any Grade III or higher toxicity related to ¹⁸F-FMISO and not related to the underlying disease.
- Patients will be considered "off-study" at the completion of study procedures. This will occur at the completion of 3 month follow up PET/CT.
- Patients may be taken off study at any time at the discretion of the Principal Investigator
- Every effort will be made to follow subjects off study for toxicity and survival.

4.7 Study Duration

With an estimated accrual of 7-8 subjects per year, it is anticipated that accrual will continue for approximately 4 years. Patients will then be followed an additional 6 months prior to final statistical analysis.

[figure not shown]
5 Study Drugs

5.1 *Description*

Nelfinavir

There are ample data available regarding the use of NFV in humans (34). The following is an excerpt of the key features.

VIRACEPT® (nelfinavir mesylate) is an inhibitor of the human immunodeficiency virus (HIV) protease. VIRACEPT Tablets are available for oral administration as a light blue, capsule-shaped tablet with a clear film coating in 250 mg strength (as NFV free base) and as a white oval tablet with a clear film coating in 625 mg strength (as NFV free base). Each tablet contains the following common inactive ingredients: calcium silicate, crospovidone, magnesium stearate, hypromellose, and triacetin. In addition, the 250 mg tablet contains FD&C blue #2 powder and the 625 mg tablet contains colloidal silicon dioxide. VIRACEPT Oral Powder is available for oral administration in a 50 mg/g strength (as NFV free base) in bottles. The oral powder also contains the following inactive ingredients: microcrystalline cellulose, maltodextrin, dibasic potassium phosphate, crospovidone, hypromellose, aspartame, sucrose palmitate, and natural and artificial flavor. The chemical name for nelfinavir mesylate is [3S-[2(2S*, 3S*), 3a,4ab,8ab]]-N-(1,1-dimethylethyl)decahydro-2-[2-hydroxy-3-[(3-hydroxy-2-methylbenzoyl)amino]-4-(phenylthio)butyl]-3-isoquinoline carboxamide mono-methanesulfonate (salt) and the molecular weight is 663.90 (567.79 as the free base). Nelfinavir mesylate has the following structural formula:

Nelfinavir mesylate is a white to off-white amorphous powder, slightly soluble in water at pH 4 and freely soluble in methanol, ethanol, 2-propanol and propylene glycol.

Pharmacokinetics

The pharmacokinetic properties of NFV were evaluated in healthy volunteers and HIV-infected patients; no substantial differences were observed between the two groups.

Absorption: Pharmacokinetic parameters of NFV (area under the plasma concentration-time curve during a 24-hour period at steady-state [AUC24], peak plasma concentrations [Cmax], morning

and evening trough concentrations [C_{trough}]) from a pharmacokinetic study in HIV-positive patients after multiple dosing with 1250 mg (five 250 mg tablets) twice daily (BID) for 28 days (10 patients) and 750 mg (three 250 mg tablets) three times daily (TID) for 28 days (11 patients) are summarized in Table 1.

Table 1
Summary of a Pharmacokinetic Study in HIV-positive Patients with Multiple Dosing of 1250 mg BID for 28 days and 750 mg TID for 28 days

Regimen	AUC ₂₄ mg•h/L	C _{max} mg/L	C _{trough} Morning mg/L	C _{trough} Afternoon or Evening mg/L
1250 mg BID	52.8 ± 15.7	4.0 ± 0.8	2.2 ± 1.3	0.7 ± 0.4
750 mg TID	43.6 ± 17.8	3.0 ± 1.6	1.4 ± 0.6	1.0 ± 0.5

data are mean ± SD

The difference between morning and afternoon or evening trough concentrations for the TID and BID regimens was also observed in healthy volunteers who were dosed at precisely 8- or 12-hour intervals. In healthy volunteers receiving a single 1250 mg dose, the 625 mg tablet was not bioequivalent to the 250 mg tablet formulation. Under fasted conditions (n=27), the AUC and C_{max} were 34% and 24% higher, respectively, for the 625 mg tablets. In a relative bioavailability assessment under fed conditions (n=28), the AUC was 24% higher for the 625 mg tablet; the C_{max} was comparable for both formulations. In healthy volunteers receiving a single 750 mg dose under fed conditions, NFV concentrations were similar following administration of the 250 mg tablet and oral powder.

Effect of Food on Oral Absorption: Food increases NFV exposure and decreases NFV pharmacokinetic variability relative to the fasted state. In one study, healthy volunteers received a single dose of 1250 mg of VIRACEPT 250 mg tablets (5 tablets) under fasted or fed conditions (three different meals). In a second study, healthy volunteers received single doses of 1250 mg VIRACEPT (5 x 250 mg tablets) under fasted or fed conditions (two different fat content meals). The results from the two studies are summarized in Table 2 and Table 3, respectively.

Table 2
Increase in AUC, C_{max} and T_{max} for Nelfinavir in Fed State Relative to Fasted State Following 1250 mg VIRACEPT (5 x 250 mg tablets)

Number of Kcal	% Fat	Number of subjects	AUC fold increase	C _{max} fold increase	Increase in T _{max} (hr)
125	20	n=21	2.2	2.0	1.00
500	20	n=22	3.1	2.3	2.00
1000	50	n=23	5.2	3.3	2.00

Table 3
Increase in Nelfinavir AUC, C_{max} and T_{max} in Fed Low Fat (20%) versus High Fat (50%) State Relative to Fasted State Following 1250 mg VIRACEPT (5 x 250 mg tablets)

Number of Kcal	% Fat	Number of subjects	AUC fold increase	C _{max} fold increase	Increase in T _{max} (hr)
500	20	n=22	3.1	2.5	1.8
500	50	n=22	5.1	3.8	2.1

NFV exposure can be increased by increasing the calorie or fat content in meals taken with VIRACEPT. A food effect study has not been conducted with the 625 mg tablet. However, based on a cross-study comparison (n=26 fed vs. n=26 fasted) following single dose administration of NFV 1250 mg, the magnitude of the food effect for the 625 mg NFV tablet appears comparable to that of the 250 mg tablets. VIRACEPT should be taken with a meal.

Distribution: The apparent volume of distribution following oral administration of NFV was 2-7 L/kg. NFV in serum is extensively protein-bound (>98%).

Metabolism: Unchanged NFV comprised 82-86% of the total plasma radioactivity after a single oral 750 mg dose of 14C-NFV. *In vitro*, multiple cytochrome P-450 enzymes including CYP3A and CYP2C19 are responsible for metabolism of NFV. One major and several minor oxidative metabolites were found in plasma. The major oxidative metabolite has *in vitro* antiviral activity comparable to the parent drug.

Elimination: The terminal half-life in plasma was typically 3.5 to 5 hours. The majority (87%) of an oral 750 mg dose containing 14C-NFV was recovered in the feces; fecal radioactivity consisted of numerous oxidative metabolites (78%) and unchanged NFV (22%). Only 1-2% of the dose was recovered in urine, of which unchanged NFV was the major component.

Special Populations

Hepatic Insufficiency: The multi-dose pharmacokinetics of NFV have not been studied in HIV-positive patients with hepatic insufficiency.

Renal Insufficiency: The pharmacokinetics of NFV have not been studied in patients with renal insufficiency; however, less than 2% of NFV is excreted in the urine, so the impact of renal impairment on NFV elimination should be minimal.

Gender and Race: No significant pharmacokinetic differences have been detected between males and females. Pharmacokinetic differences due to race have not been evaluated.

¹⁸F]FMISO

Description

1-H-1-(3-[18F]fluoro-2-hydroxypropyl)-2-nitroimidazole also known as

[¹⁸F]fluoromisonidazole or [¹⁸F]FMISO is a positron emitting radiopharmaceutical that has been studied *in vivo* in humans for measurement of regional hypoxia in a number of tumor types with positron emission tomography (PET/CT). Grierson et al described synthesis methods that yielded high specific activity ¹⁸F-FMISO for use in PET imaging studies [Grierson 1989]. Fluoromisonidazole is a congener of misonidazole which is an electron affinic drug with selective binding in cells with reduced pO₂ [Chapman 1981, 1983, Franko 1984]. An ideal hypoxia-imaging agent should distribute independently of blood flow, which is best achieved when the partition coefficient of the tracer is close to unity. Under these circumstances, imaging can be done at a time when the intracellular tracer distribution has equilibrated with the tracer in plasma near the cells. ¹⁸F-FMISO is an azomycin-based hypoxic cell sensitizer that has a nearly ideal partition coefficient and, when reduced by hypoxia, binds covalently to cellular molecules at rates that are inversely proportional to intracellular oxygen concentration, rather than by any downstream biochemical interactions. Rasey et al characterized the binding characteristics of ¹⁸F-FMISO in cells *in vitro* at various oxygen levels and in animal studies of tumors. Results demonstrated the oxygen dependent binding of radiolabeled fluoromisonidazole *in vitro* and *in vivo* and supported the use of ¹⁸F-FMISO as a quantitative hypoxia probe using the measurement of retention of ¹⁸F-FMISO in tumor vs blood and normal tissue to calculate hypoxic fraction in tumors[Rasey 1989]. The drug is a clear solution that is provided at room temperature in a sealed, sterile, pyrogen-free vial

and has an expiration time of 6 hours. The injectable dose of ^{18}F -FMISO will be ≤ 10 mCi with an expected range of 5-10 mCi at the time of injection. In the dose of ^{18}F -FMISO, only a small fraction of the FMISO molecules are radioactive. There is no evidence that nonradioactive and radioactive FMISO molecules display different biochemical behavior.

Preparation of Study Drug (^{18}F -FMISO)

The manufacturing of ^{18}F -FMISO will occur in the Cyclotron Facility of the Department of Radiology at the University of Pennsylvania. This facility manufactures USP compliant radio-labeled compounds for human use on a daily basis. The drug manufacturing will be fully documented and controlled by a set of Standard Operating Procedures (SOPs) prepared and maintained by the University of Pennsylvania Cyclotron.

Study Drug Administration: ^{18}F -FMISO

The ^{18}F -FMISO dose will be drawn and activity measured in the dose calibrator, in the imaging facility. The dose will be administered by bolus injection to the patient under the direct supervision of a Nuclear Medicine Authorized User. The injected dose of ^{18}F -FMISO for this study will be ≤ 10 mCi (approximate range for most studies is anticipated to be 5-10 mCi). A lesser dose may be injected if, in the opinion of a Nuclear Medicine Authorized User, complete imaging data could be generated. In the dose of ^{18}F -FMISO, only a small fraction of the FMISO molecules are radioactive. ^{18}F -FMISO is administered to subjects by intravenous injection. The injection and/or imaging procedure will be terminated in any patient who exhibits anaphylaxis, significant dyspnea or chest pain.

